<sup>2 Participants who withdraw voluntarily from the study prematurely are to return to the site for an ET Visit, unless withdrawal is due to death or withdrawal of consent. If the participant discontinues treatment within 3 months of the previous efficacy assessment visit, and no significant changes in cognitive status are suspected by the Investigator, clinical efficacy assessments are not required. In such cases, the site should notify the Sponsor and the Medical Monitor.

<sup>3 For the frequency of required brain MRI assessments sample collection for participants who develop ARIA-E and/or ARIA-H, see Section 5.3.1. This includes PK sample collection at the first unscheduled visit for ARIA monitoring per episode only. For the frequency of brain MRI assessments following resolution of ARIA and resumption of dosing, see Section 5.3.1.6. For management of recurrent ARIA, see Section 5.3.1.7.

<sup>4 A urine pregnancy test is required for women of childbearing potential only if the last dose of study treatment was less than 24 weeks before the clinic visit.

<sup>6 Coagulation panels, including PT, PTT, INR, and platelet count, must be performed within 35 days before the LP. If a participant, in the opinion of the Investigator, is at increased bleeding risk, the coagulation panel should be repeated within 7 days before the LP, if necessary. These repeat tests may be performed locally to facilitate a timely review of the results. Before any LP can be performed, the results of the most recent coagulation panel, concomitant medications, and overall general bleeding risk must be reviewed by the Investigator and must indicate that the LP can be performed safely. When the coagulation panel is performed at a visit that includes hematology testing, the platelet count should be done only once.

<sup>7 Before any LP can be performed, the results of the most recent coagulation panel, concomitant medications, and overall general bleeding risk must be reviewed by the Investigator and must indicate that the LP can be performed safely. An LP should not be performed if the Investigator suspects the presence of intracranial hypertension clinically or radiologically.

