# 5.3.1.2. ARIA-H (Microhemorrhage)

Treatment-emergent microhemorrhages are defined as microhemorrhages that occur while the participant is on study treatment and do not include microhemorrhages at baseline.

Table 5:	Disposition	of ARIA-H	(Microhemo	rrhage) Cases
I abic 5.	DISDUSITION	UI I XIXII XII X		mazer Cases

Clinical	Treatment-emergent Microhemorrhages (Central Read		
Symptom	Mild Moderate		Severe
Severity 	≥ 1 and ≤ 4	≥ 5 and ≤ 9	≥10
Asymptomatic	Continue dosing at current schedule	Suspend dosing. Once ARIA-H is stable, the participant may resume dosing at the same dose.	Permanently discontinue
Symptomatic	Suspend dosing. Once ARIA-H stabilizes and clinical symptoms resolve, the participant may resume dosing at the same dose.		treatment

<sup>1 Nonserious symptoms only. If serious symptoms of ARIA-H (according to the definition of serious adverse events in Section 11.1.2), treatment should be permanently discontinued.

The following study activities must be followed for participants with ARIA-H (microhemorrhage):

• Participants with ARIA-H microhemorrhage should complete all scheduled clinic visits for assessments. In addition, if ARIA-H microhemorrhage is radiographically moderate, or if symptoms are present, participants should have an unscheduled visit for an MRI every 4 weeks (± 5 days) until the ARIA-H has stabilized per the centrally read MRI.

ARIA stabilization is defined as no change or a decrease in the number or size of microhemorrhages on 2 consecutive MRIs, including the initial detection MRI. In addition, and PK samples will be collected at the first visit, scheduled or unscheduled, following an episode of ARIA.

For nonserious ARIA-H microhemorrhages and ARIA-H microhemorrhages with nonserious symptoms (according to the definition of serious adverse events in Section 11.1.2):

- Participants who develop between 1 and 4 (≥ 1 and ≤ 4) treatment-emergent microhemorrhages (mild radiographic per central MRI reading), and who have no symptoms may continue dosing per protocol.
- Participants who develop between 1 and 4 (≥ 1 and ≤ 4) treatment-emergent microhemorrhages (mild radiographic per central MRI reading), accompanied by clinical symptoms of any severity, should suspend dosing. Dosing may be resumed at the same dose once the ARIA-H is radiographically stable on follow-up MRI and clinical symptoms have resolved (in the Investigator's opinion). See Section 5.3.1.6 for dose resumption rules.

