- Participants who develop between 5 and 9 (≥ 5 and ≤ 9) treatment-emergent microhemorrhages (moderate radiographic per central MRI reading), with or without symptoms of any severity, should suspend dosing. Dosing may be resumed at the same dose once the ARIA-H is radiographically stable on follow-up MRI and clinical symptoms, if any, have resolved (in the Investigator's opinion). See Section 5.3.1.6 for dose resumption rules.
- Participants who develop 10 or more (≥ 10) treatment-emergent microhemorrhages (severe radiographic per central MRI reading), should permanently discontinue treatment.

For serious ARIA-H microhemorrhages or ARIA-H microhemorrhages with serious symptoms (according to the definition of serious adverse events in Section 11.1.2):

Participants who develop ARIA-H microhemorrhage (of any radiographic severity) that
is accompanied by serious clinical symptoms (according to the definition of serious
adverse events in Section 11.1.2) should permanently discontinue treatment.

See Section 5.3.1.6 for details on resumption of dosing when suspension occurs during the titration period and Section 5.3.1.7 for guidelines on resuming dosing after a recurrence of ARIA.

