# 5.3.1.3. ARIA-H (Superficial Siderosis)

Table 6: Disposition of ARIA-H (Superficial Siderosis) Cases

Clinical	Treatment-	ral Read)		
Symptom Mild		Moderate	Severe	
Severity 	1	2	> 2	
Asymptomatic	Continue dosing at current schedule	Suspend dosing. Once ARIA-H is stable, the participant may resume dosing at the same dose.	Permanently discontinue	
Symptomatic	Suspend dosing. Once ARIA-H stabilizes and clinical symptoms resolve, the participant may resume dosing at the same dose.		treatment	

Nonserious symptoms only. If serious symptoms of ARIA-H (according to the definition of serious adverse events in Section 11.1.2), treatment should be permanently discontinued.

The following study activities must be followed for participants with ARIA-H (superficial siderosis):

• Participants with ARIA-H superficial siderosis should complete all scheduled clinic visits for assessments and should have an unscheduled visit for an MRI every 4 weeks (± 5 days) until the ARIA-H has stabilized per the centrally read MRI. ARIA stabilization is defined as no change or a decrease in the number, size, or location of superficial siderosis on 2 consecutive MRIs, including the initial detection MRI. In addition, and PK samples will be collected at the first visit, scheduled or unscheduled, following an episode of ARIA.

For nonserious ARIA-H superficial siderosis or ARIA-H superficial siderosis with nonserious symptoms (according to the definition of serious adverse events in Section 11.1.2):

- Participants who develop 1 treatment-emergent focal area of superficial siderosis (mild radiographic per central MRI reading), and who have no symptoms may continue dosing per protocol. Participants should complete all scheduled clinic visits for assessments and have an unscheduled visit for an MRI Q4W (± 5 days) until the ARIA-H has stabilized per the centrally read MRI.
- Participants who develop 1 treatment-emergent focal area of superficial siderosis (mild radiographic per central MRI reading), with symptoms of any severity, should suspend dosing. Dosing may be resumed at the same dose once the ARIA-H is radiographically stable on follow up MRI and once clinical symptoms, if any, have resolved (in the Investigator's opinion). See Section 5.3.1.6 for dose resumption rules.

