# 5.3.1.4. Cerebral Hemorrhage > 1 cm

Participants who develop any new treatment-emergent cerebral hemorrhage > 1 cm in diameter on T2\* sequence, regardless of symptom severity during the study, will permanently discontinue treatment but should be encouraged to remain in the study. Participants should complete a FU Visit 18 weeks after the final dose, protocol-required tests and assessments at a subset of the clinic visits (see Table 3), and in addition, have an unscheduled visit for MRI every 4 weeks ( $\pm$  5 days) until the cerebral hemorrhage is confirmed stable per centrally read MRI. A cerebral hemorrhage is considered stable if there is no change or a decrease in the size or number of locations between 2 consecutive MRIs, including the initial detection MRI and the MRI performed 4 weeks ( $\pm$  5 days) later.

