5.7.1.6. ARIA Data Handling Principles

If the radiographic severity of an ARIA event increases or the event changes from asymptomatic to symptomatic, additional AE records will be added to eCRF to capture the change with new start/end AE dates (the end date of the previous record will be the start date of the next record). For analysis, records with changes in severity or symptomatic status are considered as a single ARIA event. The severity/symptomatic status for that event is defined as the worst level among all the AE records that belong to that event.

In general, the start date of the event is the earliest start date among the AE records for the ARIA event, and the end date is the latest end date.

If the same type of ARIA event happens again after the previous event has ended, then it is considered a recurrent event. Recurrent events will be referred to as the second event, the third event, etc.

If the duration based on MRI for an ARIA-E event overlaps with the duration based on MRI for an ARIA-H event, then these two ARIA events will be defined as concurrent.

If a subject experienced ARIA-E but no ARIA-H then this ARIA-E event will be defined as isolated, and similarly for ARIA-H.

The MRI duration of an ARIA event is determined based on MRI assessments. The start date is the date of the MRI assessment that initially identifies the ARIA event, and the end date is the date of the MRI assessment that shows the complete resolution of this ARIA event (in the case of ARIA-E), or ARIA being stable (in the case of ARIA-H). Stable was defined as 'No change' or 'decrease' in number, size, severity, or number of locations of ARIA-H microhemorrhage or ARIA-H superficial siderosis between 2 consecutive MRIs.

The AE eCRF data will be used as the primary source for the ARIA analysis as it contains the complete information of ARIA as well as associated symptoms. The safety MRI data collected

under the 'Neurological Examination' eCRF page will only be used for specific analyses that require information that was not available in the AE eCRF.

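### The 4-weekly follow-up MRI rule for ARIA-H microhemorrhage omits isolated asymptomatic severe cases (10 or more), so the SAP's stabilization results partly reflect scan timing that differs by grade

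*Protocol*

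**What the plan says.** Protocol Table 5 grades treatment-emergent microhemorrhage as mild (1 to 4), moderate (5 to 9) or severe (10 or more), each split by presence of symptoms.

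- **Repeat MRI.** The one instruction in Section 5.3.1.2 is: "if ARIA-H microhemorrhage is radiographically moderate, or if symptoms are present, participants should have an unscheduled visit for an MRI every 4 weeks". It runs until the central read shows stability, meaning no increase in number or size over two consecutive MRIs, the detection scan counting as the first.
- **Moderate cases.** The dosing bullet reads "moderate radiographic per central MRI reading), with or without symptoms of any severity, should suspend dosing".
- **Severe cases.** The bullet covers "treatment-emergent microhemorrhages (severe radiographic per central MRI reading), should permanently discontinue treatment". It gives no MRI instruction.
- **Superficial siderosis (5.3.1.3).** Participants at any grade "should complete all scheduled clinic visits for assessments and should have an unscheduled visit for an MRI every 4 weeks".
- **Cerebral hemorrhage > 1 cm (5.3.1.4).** Treatment stops permanently, yet participants "have an unscheduled visit for MRI every 4 weeks" until stable.
- **ARIA-E (5.3.1.1).** 4-weekly MRI applies until resolution, with no limit by grade.
- **Table 3, footnote 3.** MRI frequency for those "who develop ARIA-E and/or ARIA-H, see Section 5.3.1".

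SAP Section 5.7.1.6 dates ARIA events from MRIs. For ARIA-E, "the end date is the date of the MRI assessment that shows the complete resolution of this ARIA event"; for ARIA-H it is the MRI at which the finding is stable. SAP Table 5 (Section 5.7.1.7) lists a summary of ARIA-H stabilization.

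**The concern.** Among asymptomatic participants with microhemorrhage alone, required imaging does not increase with severity. Five to nine lesions are rescanned every 4 weeks until stable; ten or more are not. The neighbouring sections show no such break, and the protocol gives no reason for one.

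The statistical consequence is in the ARIA-H summaries. Stability cannot be recorded before a second MRI exists. If the second MRI is due after 4 weeks in one grade and months later in the next, recorded time to stability differs by grade even when the lesions behave identically. A severe participant who is never rescanned has no recorded stabilization at all. A reader of the report could take either pattern as evidence that severe microhemorrhage is slow to stabilize.

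The deviation table in SAP Section 9.2 does not help. It treats a missed scheduled or unscheduled ARIA MRI as at least major, but a scan that was never required cannot be logged as missed.

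**Working it through.** The plan states no figure here to reproduce. The check is a reading of the rule against Protocol Table 5, then a timing example.

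**Step 1. Apply the trigger (moderate, or symptomatic) to the six cells of Protocol Table 5.**

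| | Mild, 1–4 | Moderate, 5–9 | Severe, ≥ 10 |
|---|---|---|---|
| Asymptomatic | not triggered; dosing continues | triggered | **not triggered; permanent discontinuation** |
| Symptomatic | triggered | triggered | triggered |

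Four of six cells are covered. Asymptomatic mild cases are also outside the rule, but they keep dosing and keep the routine monitoring MRIs. The cell out of order is asymptomatic severe.

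**Step 2. Compare the sections.**

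| Finding | 4-weekly MRI applies to | Worst grade included? |
|---|---|---|
| ARIA-E (5.3.1.1) | all grades | yes |
| Microhemorrhage (5.3.1.2) | moderate or symptomatic | only if symptomatic |
| Superficial siderosis (5.3.1.3) | all grades | yes, although severe means permanent discontinuation |
| Cerebral hemorrhage > 1 cm (5.3.1.4) | all cases | yes, although all permanently discontinue |

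**Step 3. Look for another rule that fills the cell.** Section 5.3.1.5 applies only when ARIA-E is also present. Section 5.3.1.6 deals with suspended and resumed dosing. Section 8.1 lists severe ARIA-H as a reason to stop and sends the participant to Table 3. Table 3 has an unscheduled ARIA column with MRI, but its footnote returns the reader to Section 5.3.1. None of them supplies the frequency.

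**Step 4. Timing example.** Inputs: detection on the routine Week 22 MRI; last dose at Week 20; participant discontinues, stays in the study and follows Table 3, which has no Week 30 or Week 42 MRI column. Sections 5.2 and 8.1 require a safety follow-up 18 weeks after the last dose, and Table 2 marks a brain MRI there.

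- Severe, asymptomatic, protocol schedule: 20 + 18 = Week 38; 38 − 22 = **16 weeks** after detection.
- Moderate: 22 + 4 = Week 26; **4 weeks** after detection (± 5 days).
- Severe, post-termination schedule (SAP Section 2.2.5, follow-up 12 weeks after last dose): 20 + 12 = Week 32; 32 − 22 = **10 weeks**. That schedule also has an ET visit with MRI within 30 days of the last dose, so a scan may come sooner; the ET MRI can be omitted if another was done within 14 days.

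**Step 5. Carry this into the SAP.** Take two participants whose lesions are unchanged after detection. The moderate one is recorded as stable at 4 weeks, the severe one at 16 weeks (or 10), with no biological difference between them.

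**The case against.** **'Moderate' may mean 'at least moderate'.** The documents do not support this. Section 5.3.1.1 names both moderate and severe when it means both grades.

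**Stability matters only for resuming dosing, so a permanently discontinued participant needs no rescans.** This is the best explanation for the wording, and the section is narrower than the siderosis section in another cell too (asymptomatic mild). But cerebral hemorrhage and severe siderosis also end dosing permanently and still carry 4-weekly MRI. If the difference is intended, the protocol does not say so.

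**The practical effect is limited.** Much of this stands. The participants are not left without MRI. Symptoms, ARIA-E or siderosis would each bring in 4-weekly scanning. The post-termination schedule shortens the gap for those it reached, though not for anyone who had already completed the 18-week follow-up. The SAP plans no statistical testing and already lists MRI assessments for every microhemorrhage case, so late or absent rescans can be found by a careful reader.

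Three stronger readings are tempting and should not be drawn:

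- *An 82-week gap.* Table 3 alone shows the next MRI in its Week 104 column (104 − 22 = 82). The required 18-week follow-up MRI rules this out for a participant who stays in the study.
- *Four scans for a moderate case by Week 38.* Weeks 26, 30, 34 and 38 are a maximum. Scanning stops at stability, which a single unchanged rescan establishes.
- *False overlap with ARIA-E in the SAP's concurrent category.* The gap exists only without ARIA-E. Once ARIA-E appears, its own 4-weekly MRIs also show whether ARIA-H is stable.

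**Conclusion.** The gap is real: read as written, the protocol has no 4-weekly MRI for isolated asymptomatic severe microhemorrhage, and this does not fit its rules for ARIA-E, superficial siderosis and cerebral hemorrhage > 1 cm. In the Week 22 example the next required scan comes 16 weeks after detection under the protocol schedule, or 10 weeks under the post-termination schedule with an ET scan possibly earlier, against 4 weeks for a moderate case. The example assumes a last dose at Week 20, no symptoms, no other ARIA, and no extra MRI ordered by the investigator.

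The ARIA-H end date and stabilization summary will therefore partly measure the scan schedule, in a way that differs by grade. Incidence and severity tables and the CDR-SB summary do not depend on this stabilization timing. The number of participants affected is unknown: the 19.1% microhemorrhage incidence in Protocol Section 3.2.3.2 covers all grades, and neither document splits it. Which follow-up rule is right is for the sponsor to state.

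**What to change.** **Protocol.** Reconcile the MRI bullet and the severe bullet in Section 5.3.1.2 with Protocol Table 5 and with Sections 5.3.1.1, 5.3.1.3 and 5.3.1.4, and state the MRI follow-up intended for asymptomatic severe cases. If the difference from the other sections is deliberate, say so and give the reason. Align the Table 3 ARIA column with that statement. This is one sentence, and the unscheduled ARIA visit already exists. Dosing was offered only until 1 May 2024, so for this trial the statement serves mainly to interpret the data.

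**SAP.** In the stabilization summary, report microhemorrhage by radiographic grade. For each grade give the number with the event, the number with any MRI after detection, the number recorded as stable, and the interval from detection to first rescan. Add a note that severe cases scanned late or not at all should not be read as unstable or prolonged. The grades and MRI dates are already needed for the planned severity tables and MRI listings, so the cost is a few table rows and no new data collection.

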# 5.3.1.3. ARIA-H (Superficial Siderosis)

Table 6: Disposition of ARIA-H (Superficial Siderosis) Cases

Clinical	Treatment-	ral Read)		
Symptom Mild		Moderate	Severe	
Severity 	1	2	> 2	
Asymptomatic	Continue dosing at current schedule	Suspend dosing. Once ARIA-H is stable, the participant may resume dosing at the same dose.	Permanently discontinue	
Symptomatic	Suspend dosing. Once ARIA-H stabilizes and clinical symptoms resolve, the participant may resume dosing at the same dose.		treatment	

Nonserious symptoms only. If serious symptoms of ARIA-H (according to the definition of serious adverse events in Section 11.1.2), treatment should be permanently discontinued.

The following study activities must be followed for participants with ARIA-H (superficial siderosis):

• Participants with ARIA-H superficial siderosis should complete all scheduled clinic visits for assessments and should have an unscheduled visit for an MRI every 4 weeks (± 5 days) until the ARIA-H has stabilized per the centrally read MRI. ARIA stabilization is defined as no change or a decrease in the number, size, or location of superficial siderosis on 2 consecutive MRIs, including the initial detection MRI. In addition, and PK samples will be collected at the first visit, scheduled or unscheduled, following an episode of ARIA.

For nonserious ARIA-H superficial siderosis or ARIA-H superficial siderosis with nonserious symptoms (according to the definition of serious adverse events in Section 11.1.2):

- Participants who develop 1 treatment-emergent focal area of superficial siderosis (mild radiographic per central MRI reading), and who have no symptoms may continue dosing per protocol. Participants should complete all scheduled clinic visits for assessments and have an unscheduled visit for an MRI Q4W (± 5 days) until the ARIA-H has stabilized per the centrally read MRI.
- Participants who develop 1 treatment-emergent focal area of superficial siderosis (mild radiographic per central MRI reading), with symptoms of any severity, should suspend dosing. Dosing may be resumed at the same dose once the ARIA-H is radiographically stable on follow up MRI and once clinical symptoms, if any, have resolved (in the Investigator's opinion). See Section 5.3.1.6 for dose resumption rules.
- Participants who develop 2 treatment-emergent focal areas of superficial siderosis (moderate radiographic per central MRI reading), with or without symptoms of any severity, should suspend dosing. Dosing may be resumed at the same dose once the ARIA-H is radiographically stable on follow-up MRI and clinical symptoms have resolved (in the Investigator's opinion). See Section 5.3.1.6 for dose resumption rules.

• Participants who develop more than 2 (> 2) treatment-emergent focal area of superficial siderosis (severe radiographic per central MRI reading), with or without clinical symptoms of any severity, should permanently discontinue treatment.

For serious ARIA-H superficial siderosis or ARIA-H superficial siderosis with serious symptoms (according to the definition of serious adverse events in Section 11.1.2):

• Participants who develop ARIA-H superficial siderosis (of any radiographic severity) **accompanied by serious clinical symptoms** (according to the definition of serious adverse events in Section 11.1.2), should permanently discontinue treatment.

See Section 5.3.1.6 for details on resumption of dosing when suspension occurs during the titration period and Section 5.3.1.7 for guidelines on resuming dosing after a recurrence of ARIA.

